4.4.6 Subject Satisfaction

Subject satisfaction is a self-reported measure of satisfaction with the outcome of the index surgery. The level of satisfaction is assessed with a 5-point Likert scale. Each subject will also be asked to indicate whether (s)he would recommend the study procedure to a friend ("yes/no").

5 STATISTICAL ANALYSIS PLAN

5.1 Hypothesis Testing, Sample Size and Power

This is a single-arm, non-blinded study. The primary, quantitative endpoint is increase in thickness of the supraspinatus tendon at the device implant location.

The hypothesis being tested is that the overall thickness of the supraspinatus tendon increases by a minimum threshold identified as the objective performance criterion (OPC):

H_O: $d \le OPC$ H_A: d > OPC;

where "d" is the difference in supraspinatus tendon thickness at the location of the device at each follow-up interval (Follow-Up – Baseline).

Based upon finite element analysis (FEA) modelling, the theoretical reduction in tendon microstrains from the addition of 2 millimeters of new tendinous tissue at the tear site is 40% for articular-sided, partial thickness tears and 47% for bursal-sided tears. Data from clinical use of the device demonstrated a mean increase in tendon thickness of 2.39 ± 0.95 millimeters at one year.¹³

Sample size was estimated using PASS 2008¹⁷ and a one-sided one-sample t-test. The one-sided alpha level was set at 0.025. The value of d (mean of outcome measure) was set at 2 millimeters. Sample size calculations were made using powers of 80%, 85% and 90% and a one-sided alpha of 0.025 (non-inferiority; alpha-splitting) using a one-sample t-test.

Using a minimum OPC of 1.0 millimeter, a standard deviation of 1.0 millimeter, and 90% power, a total sample size of 13 subjects is adequate to test this hypothesis. Although adequate power is obtained with 13 subjects, to adjust for attrition and allow up to 30 evaluable subjects at 24-month follow-up meeting inclusion criterion 2A and another 30 evaluable subjects meeting inclusion criterion 2B, up to 150 subjects will be enrolled.

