3 STUDY OBJECTIVE

To evaluate bioinduction of new tissue and tendon healing after implantation of the Rotation Medical Bioinductive Implant used as either a standalone device or adjunct to surgical repair in the treatment of supraspinatus tendon tears.

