4.3 PRIMARY OUTCOME MEASURES

4.3.1 Increase in Tendon Thickness

Supraspinatus tendon thickness will be measured pre-operatively (baseline) and the total thickness of the tendon and any newly induced tissue at the implant site will be measured at each follow-up visit using magnetic resonance imaging (MRI). The mean (\pm SD) change in post-operative supraspinatus tendon thickness will be calculated at each follow-up interval.

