6.1 INCLUSION CRITERIA

Subjects enrolled in the study **MUST meet** all of the following criteria:

- 1. At least 21 years of age
- 2. Rotator cuff tear requiring surgery that meets either criterion A or B:
 - A. Medium or large partial-thickness tear or very small full-thickness tear of the supraspinatus tendon planned for standalone treatment (no surgical repair with sutures/suture anchors) with the bioinductive implant
 - B. Medium or large full-thickness tear primarily of the supraspinatus tendon planned for treatment with the bioinductive implant adjunctive to surgical repair
- 3. Chronic shoulder pain lasting longer than 3 months unresponsive to conservative therapy including, but not limited to, pain medication, physical therapy and injections
- 4. MRI of the shoulder within 60 days prior to the study procedure
- 5. Willing to comply with the prescribed post-operative rehabilitation program
- 6. Willing to be available for each protocol-required follow-up examination
- 7. Able to understand the informed consent process, including regulatory requirements such as HIPAA authorization, and document informed consent prior to completion of any study-related procedures
- 8. Ability to read, understand, and complete subject-reported outcomes in English

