7.4 PROCEDURE ASSESSMENT

During the study procedure, use of any biological agents or implants aimed at augmenting tendon-to-bone healing, excluding the Rotation Medical Rotator Cuff System, are strictly prohibited. Intra-operative data along with the following study-specific procedure information will be documented on the Procedure CRF:

- 1. Device implant time
- 2. Procedure technical success
- 3. Device implant position
 - After implantation of the device, an intra-operative photograph(s) or video recording showing the implant location of the device and all tendon and bone staples will be obtained.
- 4. Intra-operative complication (if applicable; per Section 8)

Additionally, health insurance claim forms from the study surgical procedure (e.g., UB-04) will be collected by the Sponsor. Each claim form will be de-identified and serve as its own source document.

7.5 **PROCEDURE RULES**

Subjects should be scheduled to undergo the study procedure within 60 days of baseline assessment. Device implantation will be performed in accordance with the Rotation Medical Rotator Cuff System device and instrument Instructions for Use (IFUs) and may

be performed as either a mini-open or arthroscopic procedure as determined by the surgeon and subject.

Subjects with medium or large partial-thickness tears or very small full-thickness tears of the supraspinatus tendon will undergo standalone device implantation without surgical repair of the tear.

Subjects with medium or large full-thickness tears primarily of the supraspinatus tendon will undergo device implantation adjunctive to surgical repair of the tear with sutures/suture anchors.

All subjects, regardless of supraspinatus tear size, will undergo acromioplasty and bursectomy. Removal of the periosteum at the lateral edge of the supraspinatus footprint is recommended to allow visualization of the footprint and facilitate proper device positioning. Debridement of the tendon may also be performed at the discretion of the surgeon.

Concomitant surgical treatment of the biceps tendon (i.e., tenotomy, tenodesis) and coracoacromial ligament (CA) release are also permitted during the study surgery at the discretion of the surgeon. If any other concurrent rotator cuff or shoulder surgeries not specified in this protocol are performed after the subject has been enrolled, a protocol deviation will be documented on the Protocol Deviation CRF. Wound closure is performed using standard methods.

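### In repaired full-thickness tears (criterion 2B), thickness change combines suture repair and implant, so passing the 1.0 mm OPC cannot be attributed to bioinduction

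*Combined protocol and SAP*

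**What the plan says.** Section 3 sets the objective: "To evaluate bioinduction of new tissue and tendon healing after implantation", with the implant used either alone or as an adjunct to repair.

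Thickness is the only outcome with a formal hypothesis. Section 5.1 defines d as the "difference in supraspinatus tendon thickness at the location of the device at each follow-up interval", follow-up minus baseline, and tests whether it exceeds a single OPC. It also states: "This is a single-arm, non-blinded study". The sample size rests on these values: "Using a minimum OPC of 1.0 millimeter, a standard deviation of 1.0 millimeter, and 90% power".

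Section 4.3.1 fixes the two measurements. For the first: "Supraspinatus tendon thickness will be measured pre-operatively (baseline)". For the second, "the total thickness of the tendon and any newly induced tissue at the implant site will be measured at each follow-up visit".

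Criterion 2B in Section 6.1 admits a "Medium or large full-thickness tear primarily of the supraspinatus tendon". Under Section 7.5 (Procedure Rules) these subjects "will undergo device implantation adjunctive to surgical repair of the tear with sutures/suture anchors". Criterion 2A subjects receive the implant with no suture repair. Table 7-1 schedules MRI at baseline, 3 months, 1 year and 2 years, with none between surgery and 3 months. Section 5.1 aims for up to 30 evaluable subjects at 24 months under each criterion.

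**The concern.** In 2A the operation includes no suture repair. In 2B the repair and the implant arrive together, after the baseline scan and before the first follow-up scan. Whatever thickness the repair contributes at the device site is therefore part of d, and no scan or comparator allows it to be subtracted. A 2B result above 1.0 mm could come from the implant, the repair or both, yet the natural reading of a passed OPC test is that the implant induced tissue.

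Analysing 2B on its own does not help, because the mixture is within each subject. Pooling carries it into the overall test.

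The plan recognises the distinction elsewhere: defect fill-in (Section 4.3.3) is limited to tears that were not surgically repaired. The thickness test has no such limit. The support offered beside the OPC does not cover the repaired case either. The finite element figures are for articular-sided partial-thickness and bursal-sided tears, and the earlier clinical mean of 2.39 mm (SD 0.95) is not split by repair.

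**Working it through.** **1. The plan's own figure.** Inputs from Section 5.1: assumed mean 2 mm, OPC 1.0 mm, SD 1.0 mm, one-sided alpha 0.025, power 90%. For a one-sample t-test the noncentrality is λ = (mean − OPC)/SD × √n, and power = 1 − F(t₀.₉₇₅,ₙ₋₁; n − 1, λ), where F is the noncentral t distribution function.

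- n = 12: λ = 1 × √12 = 3.464, critical t = 2.201, power 88.3%.
- n = 13: λ = 1 × √13 = 3.606, critical t = 2.179, power 91.1%.

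The stated 13 is reproduced. The arithmetic is sound; the question is what d measures in 2B.

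**2. What d contains.** Let r be the mean change at the device site from repair alone and g the mean change from induced tissue. Then:

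- 2A: d = g, so far as repair is concerned.
- 2B: d = r + g.

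The test sees only the sum.

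**3. Passing with no induced tissue.** Set g = 0 in 2B, so λ = (r − 1.0)/1.0 × √n. The documents give no value for r, so it is an assumption, shown on both sides of the OPC. At n = 30 the critical t is 2.045, so an observed mean of 1.0 + 2.045/√30 = 1.37 mm with SD 1.0 is enough to reject.

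| Assumed r (mm) | λ at n = 30 | P(reject), n = 30 | P(reject), n = 13 |
|---|---|---|---|
| 0.5 | −2.74 | <0.1% | <0.1% |
| 0.75 | −1.37 | 0.05% | 0.3% |
| 1.0 | 0 | 2.5% | 2.5% |
| 1.25 | 1.37 | 26% | 13% |
| 1.5 | 2.74 | 75% | 38% |
| 2.0 | 5.48 | 99.96% | 91% |

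Above r = 1.0 mm the rejection is correct about d and wrong only if read as bioinduction.

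**4. Repair gains below the OPC.** The table depends only on the sum r + g. If repair adds 0.75 mm and the implant adds 0.5 mm, d = 1.25 mm and the test passes 26% of the time at n = 30, although the implant's own contribution is half the OPC.

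**5. Pooling.** Take 30 subjects from 2A truly at the null (d = 1.0 mm) and 30 from 2B with repair gain only, SD 1.0 mm within each group (simulation, 40,000 trials). The pooled test passes 45% of the time at r = 1.5 mm and 95% at r = 2.0 mm. At r = 1.0 mm it passes 2.5%.

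**The case against.** **The reading site may limit r.** The documents do not say where thickness is read on the baseline scan of a full-thickness tear, and they refer to a separate MRI guideline that is not part of them. If baseline is read on existing tendon, closing the gap need not add thickness there, r could be well below 1.0 mm, and false success from repair alone would be rare. This stands. A reader might infer that the baseline site is an empty gap, that the repair enters d in full, and that the 2B test is almost bound to pass. No section says so. A repaired thickness of 2.3 to 3.0 mm can be backed out of the finite element figures, but only by assuming that strain varies inversely with thickness; taking it as r also needs a baseline reading of zero. The documents give neither, so it is not used here.

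**The objective is wider than bioinduction.** It also names tendon healing, and the hypothesis concerns overall thickness. Total thickness after repair plus implant is a fair healing outcome in 2B. This stands, and supports keeping the measure while changing its label.

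**New tissue is assessed directly.** Section 4.3.2 looks on MRI for boundaries and maturation of induced tissue in all subjects. That is relevant evidence in 2B, but it is descriptive, has no threshold, and does not enter the test.

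**Limited attribution is inherent in a single-arm post-market study.** That is so for the design, but it does not justify applying a bioinduction threshold to a quantity that includes repair. The plan foresees separate 2A and 2B groups and permits analysis by procedure type (Section 5.2), so a clean alternative is already within reach.

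**Conclusion.** The point holds as one of attribution. In 2B, and in any pool that includes 2B, rejecting d ≤ 1.0 mm does not show that the implant induced tissue. This follows from the baseline, follow-up and treatment definitions alone and needs no assumption about r.

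The size of the bias cannot be stated. With no induced tissue, SD 1.0 mm, 30 subjects and one-sided 0.025, false success runs from under 0.1% at r = 0.5 mm to 99.96% at r = 2.0 mm, and the documents do not say where in that range, or beyond it, r lies.

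Two stronger readings should be resisted. The documents do not show that repair alone does exceed the OPC. Nor is the thickness test undermined generally: 2A has no suture repair, and n = 13 is correct for the stated inputs.

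**What to change.** In Sections 4.3.1 and 5.1:

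- Make the OPC test the test of bioinduction in 2A only. The sample size of 13 is unchanged, and at the planned 30 evaluable subjects the power under the stated assumptions is 99.96% (λ = √30 = 5.48).
- Report 2B thickness change separately with a confidence interval, labelled as the combined result of repair and device under tendon healing, beside the Section 4.3.2 findings on new tissue. Do not pool 2B into the OPC test.
- State where thickness is read at baseline and at follow-up in 2B. If the MRI guideline already fixes this, cite it.
- Optionally, add a supportive 2B analysis at a matched point on tendon that was intact at baseline and lies under the implant, where that point can be found on both scans. It should not carry the formal test: the tear edge is gone after closure, the intra-operative photograph is not registered to MRI, and the number of subjects with such a point is unknown.

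The main changes are wording only, with no added scans, visits or subjects; the optional analysis needs extra readings of existing scans. The real cost is that adjunctive use loses a formal OPC claim. Recovering one would need something the design lacks, such as a repair-only arm: 23 per arm by exact t-test to detect a 1 mm device contribution at SD 1.0 mm, two-sided 0.05 and 90% power.

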5.2 INTERIM ANALYSES

Interim analyses may be conducted any time to ensure site compliance with the protocol, evaluate outcomes, meet applicable reporting requirements (e.g., possible IRB annual reports, etc.), or present/publish interim results. Subgroup analyses may be performed to assess outcomes based upon subject demographics, type/size of rotator cuff tear, type of procedure performed, or other variables that may affect study outcomes. Additionally, analyses may be stratified by study site or Investigator as necessary to support Sponsor, Investigator, or site publication plans (Section 17).

6 ELIGIBILITY CRITERIA

Subjects who meet all inclusion criteria (Section 6.1) and none of the exclusion criteria (Section 6.2) will be eligible to participate in the study.

Enrollment in the study occurs upon intra-operative confirmation that the subject meets all of the inclusion criteria and none of the exclusion criteria. Subjects who meet eligibility criteria and are enrolled will be followed per protocol through the end of the study (i.e., intent-to-treat). Subjects who do not meet the study eligibility criteria at the time of surgery will not be enrolled.

6.1 INCLUSION CRITERIA

Subjects enrolled in the study **MUST meet** all of the following criteria:

- 1. At least 21 years of age
- 2. Rotator cuff tear requiring surgery that meets either criterion A or B:
 - A. Medium or large partial-thickness tear or very small full-thickness tear of the supraspinatus tendon planned for standalone treatment (no surgical repair with sutures/suture anchors) with the bioinductive implant
 - B. Medium or large full-thickness tear primarily of the supraspinatus tendon planned for treatment with the bioinductive implant adjunctive to surgical repair
- 3. Chronic shoulder pain lasting longer than 3 months unresponsive to conservative therapy including, but not limited to, pain medication, physical therapy and injections
- 4. MRI of the shoulder within 60 days prior to the study procedure
- 5. Willing to comply with the prescribed post-operative rehabilitation program
- 6. Willing to be available for each protocol-required follow-up examination
- 7. Able to understand the informed consent process, including regulatory requirements such as HIPAA authorization, and document informed consent prior to completion of any study-related procedures
- 8. Ability to read, understand, and complete subject-reported outcomes in English

6.2 EXCLUSION CRITERIA

Subjects enrolled in the study MUST NOT meet any of the following criteria:

- 1. Massive rotator cuff tears (\geq 5 cm)
- 2. Acute rotator cuff tears less than 12 months from injury
- 3. Previous rotator cuff surgery on the index shoulder
- 4. Instability of the index shoulder
- 5. Chondromalacia of index shoulder \geq Grade 3
- 6. Fatty infiltration of the index shoulder rotator cuff muscle \geq Grade 2

- 7. Calcification of the index shoulder rotator cuff
- 8. Genetic collagen disease
- 9. History of insulin dependent diabetes
- 10. History of auto-immune or immunodeficiency disorders
- 11. History of chronic inflammatory disorders
- 12. Oral steroid use in last 2 months or injectable steroid use in last 4 weeks
- 13. History of heavy smoking (> 1 pack per day) within last 6 months
- 14. Hypersensitivity to bovine-derived materials
- 15. Females of child-bearing potential who are pregnant or plan to become pregnant during the course of the study
- 16. Currently involved in any injury litigation or worker's compensation claims relating to the index shoulder
- 17. Enrolled, or plans to enroll, in another clinical trial during this study that would affect the outcomes of this study
- 18. History of non-compliance with medical treatment, physical therapy/rehabilitation, or clinical study participation
- 19. History of cognitive or mental health status that interferes with study participation

7 STUDY ASSESSEMENTS

The schedule of protocol-required study assessments is provided in **Table 7.1**. Adverse event (AE) reporting as required and defined in **Section 8** begins at the time of enrollment (i.e. intra-operative confirmation of eligibility) and concludes at the end of the study.

	Baseline	Procedure	3-Month	1 Year	2 Year
Study Evaluation	Within 60 Days of Surgery	Within 60 Days of Baseline	± 15 days	± 45 days	±90 days
Informed Consent	\checkmark				
Medical History & Exam	\checkmark				
Eligibility Assessment	\checkmark	✓1			
Enrollment (Date of Surgery)		✓			
MRI	\checkmark^2		\checkmark^2	√ ²	\checkmark^2
ASES Survey	√ ³		√ ³	√ ³	√ ³
Constant-Murley Survey	\checkmark		\checkmark	✓	\checkmark
Procedure Data		✓			
Medications	\checkmark^4	✓4	\checkmark^4	\checkmark^4	✓4
Adverse Events		✓ ⁵	√ ⁵	√ ⁵	√5
Recovery/Satisfaction			✓	✓	✓
Questionnaire					
Revision/Additional			√ ⁶	√ ⁶	√ ⁶
Shoulder Surgery					

 Table 7-1: Schedule of Study Assessments

¹Eligibility confirmation will be performed at the time of the study surgery to ensure the rotator cuff tear location/size meets eligibility criteria. Patients whose rotator cuff tears do not meet study eligibility criteria will not be enrolled in the study.

²Each study MRI must be performed in accordance with the MRI study guideline.

³The ASES-Patient Assessment is required. The ASES-Physician Assessment (ROM; strength) is optional as strength and ROM assessments are included in the Constant-Murley survey.

⁴Only prescription medications to treat the index shoulder will be recorded.

⁵Non-serious AEs will only be recorded if they are classified as either possibly or definitely related to either the study device or the study procedure.

⁶Any additional surgical intervention performed on the index shoulder will be reported.

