7.1 ELIGIBILITY ASSESSMENT

Subjects are considered eligible for this study if they meet all of the inclusion criteria and none of the exclusion criteria as defined in **Section 6.1** and **Section 6.2**. The Investigator, co-Investigator, or sub-Investigator performing the study surgery will confirm eligibility at the time of the study surgery based upon intra-operative evaluation of the rotator cuff tear characteristics.

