7.2 ENROLLMENT

Enrollment in the study occurs upon intra-operative confirmation that the subject meets all of the inclusion criteria and none of the exclusion criteria. **Patients whose rotator cuff tears do not meet study eligibility criteria at the time of the study procedure will undergo tendon repair at the discretion of the surgeon (with or without use of the Rotation Medical Rotator Cuff System) and will not be enrolled in the study**. Subjects who meet eligibility criteria will be considered enrolled into the study regardless of whether or not the device was successfully implanted. The date of the study surgery is defined as the enrollment date and all subjects who are enrolled in the study will be followed per protocol unless voluntary consent is withdrawn. All subjects enrolled into the study will be identified through a unique identifier.

7.3 **BASELINE ASSESSMENT**

The following activities must be conducted within 60 calendar days prior to enrollment:

- 1. Obtain written informed consent.
- 2. Obtain a medical history.
- 3. Perform an MRI per the Sponsor imaging guidelines.
 - Provide the Sponsor with a de-identified digital copy of, or access to, the MRI.
- 4. Assess subject eligibility based on inclusion/exclusion criteria defined in Section 6.1 and 6.2.
- 5. Administer the Constant-Murley shoulder survey.
 - *Range of motion (ROM) should be measured with a goniometer and strength should be measured with a dynamometer.*
- 6. Administer the ASES shoulder survey.
 - Completion of the ASES patient assessment section is required. Completion of the ASES physician assessment section is optional since ROM and strength are assessed during administration of the Constant-Murley survey.
- 7. Record prescription medications.
 - *Record any prescription medications the subject is taking at the time of the baseline visit to treat his/her index shoulder.*

All baseline assessments will be documented on their respective Case Report Forms (CRFs).

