8 ADVERSE EVENT DEFINITIONS AND REPORTING

Adverse events are to be reported from the time of enrollment through the last study follow-up visit.

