8.3 UNANTICIPATED ADVERSE DEVICE EFFECT (UADE)

An Unanticipated Adverse Device Effects (UADE) is any serious adverse effect on health or safety, or any life-threatening problem or death caused by, or associated with, a device, if that effect was not previously identified in nature, severity, or degree of incidence in protocol, subject informed consent form, or application, or any other unanticipated serious problem associated with a device that relates to the rights, safety, or welfare of subjects. Anticipated adverse events are listed as known risks in **Section 12.1**.

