8.4 Assessing, Recording and Reporting AEs, SAEs, and UADEs

Only non-serious AEs that are classified by the Investigator as either device-related or procedure-related will be reported. All SAEs, regardless of relationship to the Rotation Medical Rotator Cuff System, and all UADEs will be reported.

An AE may be volunteered spontaneously by the subject or discovered as a result of questioning or physical examination by the Investigator or study staff. The following information should be reported on the Adverse Event CRF as soon as the Investigator becomes aware of the event and updated as needed until event resolves:

- Date of AE onset
- Date the Investigator became aware of the AE
- Main complaints/symptoms of the AE
- Relationship to the study device
- Relationship to the study procedure
- Status of the adverse event

Source documents (e.g., procedural notes, treatment notes, or a signed clinical summary) may be required as supporting documentation for the reported AE.

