12 RISKS AND BENEFITS

12.1 RISKS AND RISK MITIGATION

Study patients will be informed of all known potential side effects and complications associated with the study assessments and study procedure prior to enrollment in the study.

There are no known incremental risks to the subject for participating in the study. The risks associated with participating in this study are the same as if the patient is treated outside of the study using the same commercially-available device and include the following potential risks of rotator cuff surgery performed under general or regional anesthesia:

- Tissue inflammation
- The need for repeated surgery because tendons do not heal properly or tear again
- Pain or stiffness that won't go away
- Fever and/or infection
- Complication from anesthesia
- Nerve or blood vessel damage
- Adverse reaction to device

In addition, subjects will be required to undergo MR imaging. MRI is generally a welltolerated procedure and there is no ionizing radiation involved with MR imaging The potential risks are minimal and include claustrophobia, coil element heating and peripheral nerve stimulation, although the latter two are considered highly unlikely, given that the subjects will be imaged within preset safety guidelines to eliminate peripheral nerve stimulation. Coil element heating ranges from a mild sensation of heat to a potential burn. This is considered highly unlikely, as the coils have all undergone extensive testing and clinical use, and special pads are placed surrounding all contact points.

All Investigators will undergo training and subjects will be screened and evaluated for medical histories/conditions that may compromise safe, successful completion of any of the study assessments or performance of the device. Subjects with a known hypersensitivity to bovine-derived materials will not be enrolled in the study.

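### As written, adverse event reporting opens at intra-operative confirmation of eligibility, so events between the start of anaesthesia and that moment may be missing from the procedure-related rate, and sites may apply the rule differently

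*Combined protocol and SAP*

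**What the plan says.** - **Start of reporting.** Section 7 states that adverse event reporting "begins at the time of enrollment (i.e. intra-operative confirmation of eligibility) and concludes at the end of the study". Section 8 opens with the same start: "Adverse events are to be reported from the time of enrollment through the last study follow-up visit".
- **Moment of enrollment.** Section 7.2: "Enrollment in the study occurs upon intra-operative confirmation that the subject meets all of the inclusion criteria and none of the exclusion criteria". Under Section 7.1 the operating surgeon confirms eligibility "based upon intra-operative evaluation of the rotator cuff tear characteristics".
- **Date of enrollment.** Section 7.2 also says: "The date of the study surgery is defined as the enrollment date". Table 7-1 labels the enrollment row by the date of surgery and ticks adverse events at the procedure visit.
- **Forms.** Section 7.4 puts a line for complications during surgery on the Procedure CRF, but refers that line back to Section 8. The items that Section 8.4 lists for the Adverse Event CRF include "Date of AE onset" and no clock time.
- **Known risks.** Section 8.3 says: "Anticipated adverse events are listed as known risks in" Section 12.1. That list includes "Complication from anesthesia" and damage to nerves or blood vessels.
- **Outcome.** Section 4.4.1 makes safety a secondary outcome. It covers deaths, all serious events, non-serious events related to the device or procedure, and unanticipated device effects, and it is summarised by relation to device or procedure.

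**The concern.** A procedure-related rate is normally read as covering the whole procedure, from anaesthesia onward. Here the window is tied to a moment inside the operation. The patient has by then already been exposed to some of the risks that the plan itself names. An event in that interval could be serious and clearly due to the procedure, and still not be reportable under Sections 7 and 8.

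Two things are at stake. First, the rate in Section 4.4.1 may be understated, and an omission of this kind can only lower the count. Second, the plan does not give every site the same answer for a same-day event before confirmation. Up to 15 sites contribute (Section 4.1), and Section 14.2 names uniform data collection as an aim of training.

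**Working it through.** The plan gives no expected adverse event rate, so there is no safety figure to reproduce. The sample size of 13 in Section 5.1 rests on tendon thickness and is not affected. The check is a comparison of the text, followed by an illustration of size.

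**Step 1: the order of events.** Section 12.1 describes the surgery as done under general or regional anaesthesia. Section 7.1 requires the tear to be assessed during surgery. Section 7.2 places enrollment at that assessment, and Sections 7 and 8 start reporting at enrollment. The sequence is therefore: anaesthesia, surgical access, view of the tear, confirmation, start of reporting. The interval before confirmation is outside the window.

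**Step 2: which events are affected.** Only events with onset before confirmation. An anaesthetic, nerve or vessel event that begins later, during implantation or repair or after surgery, is inside the window. It is reportable if serious or if classed as device- or procedure-related (Section 8.4).

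**Step 3: do other sections close the gap?**

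| Text | Pulls towards | Settles it? |
|---|---|---|
| Section 7: reporting starts at the intra-operative confirmation | Excluding earlier events | Explicit, defined as a moment |
| Section 7.2 and Table 7-1: enrollment date is the day of surgery | Including same-day events | No; gives a date, while Section 7 gives a moment |
| Section 7.4: complication line on the Procedure CRF | Including them | No; it refers to Section 8, which starts at enrollment |
| Section 8.4: onset recorded by date | Including them in practice | No; events before and after confirmation cannot be told apart |

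The literal rule excludes the interval, while the date-level fields could lead a site to include it. The text does not decide between them.

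**Step 4: size, by assumption only.** Let q be the probability that an enrolled subject has a serious or procedure-related event before confirmation, and suppose that none is recorded. With N subjects, the expected number missed is N × q, and the chance of at least one is 1 − (1 − q)^N. N = 150 is the ceiling in Section 4.1. N = 60 is a smaller case, from the two groups of 30 evaluable subjects in Section 5.1. The values of q are assumptions.

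| q (assumed) | Missed, N = 150 | At least one, N = 150 | Missed, N = 60 | At least one, N = 60 |
|---|---|---|---|---|
| 0.5% | 150 × 0.005 = 0.75 | 53% | 0.3 | 26% |
| 1% | 150 × 0.01 = 1.5 | 78% | 0.6 | 45% |
| 2% | 150 × 0.02 = 3.0 | 95% | 1.2 | 70% |

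These are upper figures for each q, because sites that work by date would record some of the events.

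**The case against.** The strongest reply is that this is a descriptive, secondary outcome in a post-market study of cleared devices, with a population defined consistently at intra-operative confirmation. The day of surgery is the enrollment date, adverse events are ticked at the procedure visit, and complications during surgery have their own line on a form. A sensible site would record an induction event on the day of surgery. This stands in part: it makes an undercount possible and not certain. It does not remove the explicit definition in Section 7, and the complication line leads back to that definition.

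Four stronger readings are tempting and are not supported:

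- **A reader might infer that anaesthetic and access events are left out as a class.** Only those starting before confirmation are affected. Surgical access is not itself an item in Section 12.1. The nearest item, nerve or vessel damage, is not confined to access.
- **A reader might infer that the rate is bound to be too low.** The date-level enrollment definition and the date-only onset field leave room for such events to be counted.
- **A reader might extend the point to the baseline MRI.** A non-serious MRI event would be reportable only if classed as related to the device or the study procedure, which is the surgery (Section 8.4 and the Table 7-1 footnote). An earlier start would not change that.
- **A reader might infer that early complications lead surgeons not to enroll.** The grounds in Section 7.5 are tear size, tissue quality or a need for surgery beyond what is permitted. A complication is not among them. Patients who are not enrolled are in neither the numerator nor the denominator, so their absence alone does not bias the rate among enrolled subjects. The documents require no record of them, which justifies an optional listing and nothing more.

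**Conclusion.** The point holds in limited form. As written, serious or procedure-related events that start and are recognised between the start of anaesthesia and confirmation of eligibility fall outside the reporting window, so the procedure-related rate may be understated. Sections 7, 7.2, 7.4, 8 and 8.4 together leave it unclear whether same-day events before confirmation count, and sites may differ.

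The documents do not allow the amount to be computed. The range of 0.75 to 3 events in 150 depends on an assumed 0.5% to 2%, on full enrollment and on no site recording such events. No efficacy or sample-size figure changes. This is an inexpensive improvement to a secondary outcome and does not threaten the study's main conclusion.

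**What to change.** Reconcile Sections 7, 7.2, 7.4 and 8. In Sections 7 and 8, state that for enrolled subjects adverse event recording starts no later than the start of anaesthesia for the study surgery. State that the complication line in Section 7.4 follows the same start. The definition of enrollment in Section 7.2 can stay as it is, because the recording window no longer depends on it. Clinical management is untouched.

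Optionally, add a short separate listing of serious events in consented patients who were anaesthetised for the study surgery but not enrolled, kept out of the rate.

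Cost: about one sentence in each of Sections 7 and 8, a cross-reference in Section 7.4 and a few more event forms. The optional listing costs more, because Section 7.2 gives identifiers, and Section 13.1 gives CRFs, to enrolled subjects. A simple identifier and a short form for non-enrolled patients would be needed.
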